4. BMI >45
5. Pregnant or nursing
6. Chronic home opioid usage
7. LVEF < 30%
8. Low cardiac output requiring mechanical or inotropic support
9. End-stage renal disease
10. Cirrhosis
11. Re-do sternotomy
12. Endocarditis

Data elements

Patient Characteristics:

1. Age
2. Gender
3. BMI
4. Tobacco use
5. Chronic lung disease
6. Diabetes
7. HTN
8. HDL
9. Ethnicity (Hispanic & not Hispanic)
10. Race (Caucasian, African Americans, Asians and others)
11. CKD
12. CVA
13. Chronic home NSAID use (excluding ASA)

Intraoperative Variables:

1. Type of procedure being performed
2. Prior procedures performed

Postoperative Variables:

Time to extubation, time to ambulation, time to oral diet, return of bowel function (bowel movement), postoperative atrial fibrillation incidence (through discharge), and intensive care unit (ICU) length of stay (LOS) and overall LOS. Maximum incentive spirometer maximum volume at 24, 48 and 72 hours, Confusion assessment method (CAM) at 24, 48 and 72 hours, post op opioid usage up to 72 hours post op. If additional days of post-op opioid usage is documented in the existing medical record, this may be used also. CAMs are performed by the blinded research coordinator.

Pain scores (Scale 0-10) at 1, 2, 4, 8, 12, 24, 36, 48, 60, and 72 hours after ICU arrival for extubated patients and CPOT scores (Scale 0-8) for intubated patients

Adverse Events: Allergic reaction, pneumothorax, pericardial tamponade, vascular injury, hematoma, intravascular injection, wound infection, paresthesia, persistent numbness. These adverse events will be monitored and reported from the start of the study procedure to discharge (study termination).

Protocol Deviations: If certain data elements are not in the existing medical record and were not collected, this is not a protocol deviation. Nevertheless, all effort will be made to collect these data points.

Funding: CVRRC

Journals in which you plan to publish or meetings where abstracts will be submitted: TBD

Risks and Benefits

Risks: The risks are the same as the Standard of Care surgery performed outside this study. This is discussed in the ICF. A confidentiality breach is a risk associated with research. However, all data collection protocols follow HIPAA guidance.

Benefits: If participants receive the drug, they could experience less pain than those that don't receive the drug. However, not all participants are likely to benefit from the proposed research. The investigators will benefit from the knowledge gained, as it will provide deepened insight on the main challenges, advantages and disadvantages of the procedure.

Data Analytic Methods

The mean, standard deviation, median, and interquartile ranges of narcotic usage (in morphine equivalent units) will be reported for each group. The difference of narcotic usage between the two groups will be reported as a single value. Additional variables analyzed in this study include the following:

Patient Characteristics:

1. Age
2. Gender
3. BM
4. Tobacco use
5. Chronic pain medication usage
6. Diabetes

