Title: Regional Blockade of the Sternum with Liposomal Bupivacaine Prior to Incision Decreases Opioid Use in Patients undergoing Cardiac Surgery

Personnel:

- a) Principal Investigator: [name]
- b) Sub-Investigators:
 - i) [name]
 - ii) [name]
 - iii) [name]
 - iv) [name]
 - v) J. [name]
 - vi) [name]
 - vii) [name]
 - viii) [name]
 - ix) [name]
 - x) [name]
 - xi) [name]
 - xii) [name]

Background:

Prolonged and excessive narcotic usage in the postoperative setting has been linked to multiple complications. Use of complimentary pain management techniques such as regional analgesia can reduce postoperative pain and narcotic usage. This can enhance patient recovery and improve quality of life in the immediate postoperative period. [1] Previous research investigating the benefits of local analgesia during cardiac surgery have been limited by the sparse amount of single-center randomized controlled trials, particularly evaluating the use of para-sternal injections.

Of the available studies, the use of local analgesia injections compared to controls has led to improved pain scores and overall decreased perioperative opioid usage. Studies have shown this efficacy using 0.2% ropivacaine, [2] 0.75% ropivacaine, [3] and 0.53% liposomal bupivacaine [4] all compared to control groups receiving normal saline injections in the para-sternal area. These studies all used injections just prior to sternal closure and no significant evidence is available for the use of ultrasound-guided regional block of the sternum prior to surgical incision. Injection of analgesia prior to surgical incision has been shown to decrease postoperative pain compared to injection after surgical closure. [5]

Hypothesis/Aims:

We hypothesize that injection of 1.3% liposomal bupivacaine and 0.5% bupivacaine (20mL dose) as a sternal block prior to surgical incision will lead to decreased pain and opioid usage in the intraoperative and postoperative setting for patients undergoing upper mini- and median sternotomy compared to controls (normal saline block).

Aim 1: To demonstrate decreased postoperative opioid usage and decreased pain scores in the postoperative setting in the treatment group compared to controls.

The amount of opioid medications used will be recorded during the routine postoperative course. Pain scores, set by a validated system, will be obtained daily during the routine postoperative course.

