Aim 2: To demonstrate decreased intraoperative opioid usage in the treatment group compared to controls

Aim 3: To demonstrate improvement in key clinical components closely linked to narcotic usage.

Multiple variables specific to opioid usage will be recorded during the routine postoperative setting. These included, but are not limited to: time to extubation, incentive spirometer volume, return of bowel function, postoperative atrial fibrillation incidence, delirium and intensive care unit (ICU) and overall lengths of stay (LOS).

Methods

This is an investigator-initiated prospective randomized study with an 18-month patient accrual period and patient follow-up period dependent on postoperative length of stay following surgery.

Regional Block: Liposomal Bupivacaine (1.3%) solution (20 mL dose) is proposed for use during this study. This solution has demonstrated increased efficacy in prolonged analgesia following injection. This solution will be injected as an ultrasound-guided subpectoral interfacial plane block.

Normal Saline: Normal saline (0.9%) will be used as the control solution for patients not receiving the liposomal bupivacaine solution. Injection procedure of this solution will be identical to that of the liposomal bupivacaine solution.

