Procedures: Patients undergoing a surgical procedure through mini- or full sternotomy will be considered for inclusion in this study. Qualified patients will be randomized 1:1 to a liposomal bupivacaine sternal block or a normal saline block. An unblinded research coordinator will use a password-protected spreadsheet to randomly generate the subject's randomization assignment. The unblinded coordinator will communicate the information to the unblinded anesthesiologist who will perform the block. This ensures the intraoperative (including a blinded anesthesiologist and surgeon) and postoperative staff (including the blinded research coordinator) will remain blind to the randomization assignment. The subject will also be blinded to the assignment. The amount of opioid medications given by the anesthesia team during the procedure will be recorded. Anesthesiologists will be encouraged to standard of care early extubation. There will be no deviation from routine surgical procedures following injection of para-sternal solution prior to surgical incision. Patients are considered part of the research study until they are discharged. After discharge, patients can be told which block they were given and the blinded coordinator can be unblinded to review all medical records.

Study Population

Patients undergoing a surgical procedure through mini- or full sternotomy from 7/1/2019 at THHBP will be included in this data set. A total of 150 patients is proposed for this study.

Inclusion Criteria:

1. Age greater than 18 years
2. Undergoing a surgical procedure through mini- or full sternotomy.

Exclusion Criteria:

1. Clinical instability

2. Allergic to liposomal bupivacaine solution or any of its ingredients
3. Maximum-allowed dosage of local analgesia will be exceeded by the injection amount of liposomal bupivacaine used in this study (<50 kg).

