4. ICU LOS
5. Total LOS from date of sternotomy
6. Return of bowel function
7. Postoperative atrial fibrillation

8. Maximum spirometry at 24, 48, 72 hours post op
9. CAM at 24, 48, 72 hours post op
10. Pain Scores (Scale 0-10) at 1, 2, 4, 8, 12, 24, 36, 48, 60, and 72 hours after ICU arrival for extubated patients and CPOT scores (Scale 0-8) for intubated patients
11. Post op opioid usage up to 72 hours post op

Standard descriptive statistics will be used throughout (mean, range, standard deviation, and median, IQR), with comparative statistics for normally and non-normally distributed data with $p < 0.05$ considered as significant. For categorical variables, 2 Sample t-test or chi-squared test will be used to determine statistical significance. For continuous variables, logistic regression will be used to determine the value of significance to variables with postoperative outcomes. Depending on the enrollment rate, the stratification of data based on the type of sternotomy (full or mini) could be performed and analyzed respectively.

References

1. Bignami, E., et al., *Perioperative pain management in cardiac surgery: a systematic review*. Minerva Anestesiol, 2018. 84(4): p. 488-503.
2. Dowling, R., et al., *Improved pain control after cardiac surgery: results of a randomized, double-blind, clinical trial*. J Thorac Cardiovasc Surg, 2003. 126(5): p. 1271-8.
3. Barr, A.M., E. Tutungi, and A.A. Almeida, *Parasternal intercostal block with ropivacaine for pain management after cardiac surgery: a double-blind, randomized, controlled trial*. J Cardiothorac Vasc Anesth, 2007. 21(4): p. 547-53.
4. Lee, C.Y., et al., *A Randomized Controlled Trial of Liposomal Bupivacaine Parasternal Intercostal Block for Sternotomy*. Ann Thorac Surg, 2019. 107(1): p. 128-134.
5. Labrum, J.T.t. and A.M. Ilyas, *Preemptive Analgesia in Thumb Basal Joint Arthroplasty: Immediate Postoperative Pain with Preincision versus Postincision Local Anesthesia*. J Hand Microsurg, 2017. 9(2): p. 80-83.

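### Does the optional use of opioid days charted after 72 hours leave the narcotic comparison undefined?

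*Combined protocol and SAP*

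**What the plan says.** Data elements, under Postoperative Variables, collects postoperative opioid use up to 72 hours and then adds "If additional days of post-op opioid usage is documented in the existing medical record, this may be used also". Data Analytic Methods summarises narcotic use in morphine equivalents (MME) by group and states "The difference of narcotic usage between the two groups will be reported as a single value". It then lists additional variables; item 11 of the postoperative list is "Post op opioid usage up to 72 hours post op".

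The aims are wider. The hypothesis expects "decreased pain and opioid usage in the intraoperative and postoperative setting". Aim 1 covers postoperative use, recorded over the ordinary hospital course with no limit in hours. Aim 2 is separate: "To demonstrate decreased intraoperative opioid usage in the treatment group compared to controls". Procedures provides the data for it: "The amount of opioid medications given by the anesthesia team during the procedure will be recorded".

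Methods describes a "patient follow-up period dependent on postoperative length of stay following surgery", and Procedures says "Patients are considered part of the research study until they are discharged". Pain scores are timed from ICU arrival; the 72-hour opioid window has no stated starting point.

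**The concern.** Postoperative opioid use comes first in Aim 1, yet the sentence reporting the difference between groups names neither a time window nor the components. Three quantities could be meant: the 72-hour postoperative total, the total to discharge, or either of these with intraoperative use added.

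The choice between the first two is more than a label. Opioid days after 72 hours are observed only in patients who have not gone home. If the block shortens stay, as Aim 3 hopes, the to-discharge total falls even when opioid need per day is the same in both arms. If the effect is mainly early, later days add noise and dilute it. If the window were chosen after seeing the data, the 5% significance level would no longer hold exactly.

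**Working it through.** **Which reading does the text support?**

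- *Window.* The collection list and item 11 of the analysis list both give 72 hours. Later days appear in no analysis item, and the sentence permitting them presents them as an addition to the 72-hour data, not a replacement.
- *Intraoperative use.* Aim 1 is postoperative, Aim 2 is intraoperative, and item 11 is limited to postoperative use. The hypothesis names two settings; it does not define a sum. Power figures for a combined total would describe an endpoint that nobody proposes.
- *Clock start.* Timing from ICU arrival or from the end of surgery applies alike to both arms, whose postoperative staff are blinded. No effect on the comparison has been shown.

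**Is there a plan figure to reproduce?** No. The 150 patients (75 per arm at 1:1) come without an effect size, SD or power, so no stated figure depends on the window.

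**False positives from choosing between the windows.** Let *a* be the 72-hour total and *b* the later use, with correlation ρ. With no treatment effect, the two test statistics correlate as

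r = (σa² + ρσaσb) / (σa √(σa² + σb² + 2ρσaσb)).

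| Assumed σa, σb, ρ | r | P(at least one p < 0.05) |
|---|---|---|
| 1, 1, 0 | 1/√2 = 0.707 | 8.3% |
| 1, 0.5, 0 | 1/√1.25 = 0.894 | about 7.0% |
| 1, 0.5, 0.6 | 1.3/√1.85 = 0.956 | 6.4% |

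A separate simulation with skewed data and Wilcoxon tests gave 5.6–8.3%. Allowing four readings, two of which add intraoperative use, gave about 8–13%. Those two are the readings that no section proposes.

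**Effect of a shorter stay.** All inputs are assumptions: 72-hour use log-normal with median 60 MME and log-SD 0.8; stay Normal(6, 1.5) days; later daily use a fraction f of the 72-hour daily average.

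- Mean 72-hour use = 60 × exp(0.8²/2) = 82.6 MME, or 27.5 per day.
- With no effect on opioid rate and stay shorter by d days, the to-discharge difference is about d × f × 27.5. For d = 0.5 and f = 0.3 this is 4.1 MME; for d = 1 and f = 0.6 it is 16.5. Simulation, which also allows discharge before 72 hours, gave about 4 to 17.
- The to-discharge total was then significant in 6–17% of simulated trials when later use is proportional to early use, and in 8–27% when the two are independent. The 72-hour total stayed near 5%.
- With f = 0.1 and d = 0.5, the to-discharge rate was about 5–6%. The 27% figure needs a full day's shorter stay, f = 0.6 and independence together.

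**Power for a 30% fall in the first 72 hours, equal stay.** The 72-hour total has about 75%. The to-discharge total has:

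| Effect after 72 h | Later use proportional | Later use independent |
|---|---|---|
| None | 34–50% | 47–62% |
| Half persists | 53–63% | 71–78% |
| All persists | 73–74% | 89–90% |

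**Discharge before 72 hours.** In the shorter-stay runs, setting the unobserved hours to zero gave rejection of 0.043–0.053 for the 72-hour total. Carrying forward the last 24-hour rate gave 0.043–0.051. Neither rule moves the result noticeably from 5%.

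**The case for a change.** The strongest case for a change is that the 72-hour reading is an inference. Item 11 sits in a list introduced as additional to the narcotic comparison, so strictly it does not define that comparison. Aim 1 has no limit in hours. The permissive sentence speaks of using the later days, not merely describing them. Because those days depend on length of stay, a to-discharge total mixes opioid need with another outcome, and a few sentences would settle the matter using data already collected.

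The textual point stands: no section expressly ties the reported difference to a window, and a to-discharge total does partly reflect length of stay. It does not follow that the plan would give a wrong answer. A lower to-discharge total is a real fall in inpatient opioid use, provided it is labelled as such. Aim 1's wording also gives the longer window some basis, so preferring 72 hours is partly a trade-off: it avoids dependence on stay, but gives up power if the effect lasts. The low cost of a clarification does not show that the present text misleads.

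**Conclusion.** No change to the plan is needed. What is missing is a statement of the role of an optional extension. The natural way to fill the gap is to report the 72-hour postoperative total, show later charted days separately and labelled as such, and report intraoperative use under Aim 2.

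If an analyst instead chose between the two postoperative windows after seeing the data, the false-positive rate would be about 6–8% against a nominal 5%. A to-discharge total could reach significance through shorter stay alone. Across the scenarios with later daily use at 10–60% of the early rate and stay shorter by 0.5 to 1 day, that happened in about 5–27% of simulated trials, with the upper end needing an extreme combination. All these sizes rest on assumed opioid use, variability and length of stay, because the documents state none of them. A reader of the results should check that the reported narcotic difference is labelled with its window.

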7. HTN
8. HLD
9. Race & Ethnicity
10. CKD
11. CVA

Intraoperative Variables:

1. Type of procedure being performed
2. Prior procedures performed

Postoperative Variables:

1. Time to extubation
2. Time to ambulation
3. Time to oral diet (solid foods)
4. ICU LOS
5. Total LOS from date of sternotomy
6. Return of bowel function
7. Postoperative atrial fibrillation

8. Maximum spirometry at 24, 48, 72 hours post op
9. CAM at 24, 48, 72 hours post op
10. Pain Scores (Scale 0-10) at 1, 2, 4, 8, 12, 24, 36, 48, 60, and 72 hours after ICU arrival for extubated patients and CPOT scores (Scale 0-8) for intubated patients
11. Post op opioid usage up to 72 hours post op

Standard descriptive statistics will be used throughout (mean, range, standard deviation, and median, IQR), with comparative statistics for normally and non-normally distributed data with $p < 0.05$ considered as significant. For categorical variables, 2 Sample t-test or chi-squared test will be used to determine statistical significance. For continuous variables, logistic regression will be used to determine the value of significance to variables with postoperative outcomes. Depending on the enrollment rate, the stratification of data based on the type of sternotomy (full or mini) could be performed and analyzed respectively.

References

1. Bignami, E., et al., *Perioperative pain management in cardiac surgery: a systematic review*. Minerva Anestesiol, 2018. 84(4): p. 488-503.
2. Dowling, R., et al., *Improved pain control after cardiac surgery: results of a randomized, double-blind, clinical trial*. J Thorac Cardiovasc Surg, 2003. 126(5): p. 1271-8.
3. Barr, A.M., E. Tutungi, and A.A. Almeida, *Parasternal intercostal block with ropivacaine for pain management after cardiac surgery: a double-blind, randomized, controlled trial*. J Cardiothorac Vasc Anesth, 2007. 21(4): p. 547-53.
4. Lee, C.Y., et al., *A Randomized Controlled Trial of Liposomal Bupivacaine Parasternal Intercostal Block for Sternotomy*. Ann Thorac Surg, 2019. 107(1): p. 128-134.
5. Labrum, J.T.t. and A.M. Ilyas, *Preemptive Analgesia in Thumb Basal Joint Arthroplasty: Immediate Postoperative Pain with Preincision versus Postincision Local Anesthesia*. J Hand Microsurg, 2017. 9(2): p. 80-83.

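### The plan defines no single treatment contrast for the three incentive spirometer readings and names a method that does not fit them, so an Aim 3 claim could rest on any one reading

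*Combined protocol and SAP*

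**What the plan says.** - Hypothesis/Aims states the objective as "Aim 3: To demonstrate improvement in key clinical components closely linked to narcotic usage". Among the components it names spirometry once: "time to extubation, incentive spirometer volume, return of bowel function". It does not define when a component has improved.
- Data elements, Postoperative Variables, collects "Maximum incentive spirometer maximum volume at 24, 48 and 72 hours", so each patient can contribute three readings.
- Data Analytic Methods introduces its list with "Additional variables analyzed in this study include the following". Item 8 under Postoperative Variables is "Maximum spirometry at 24, 48, 72 hours post op". The readings are therefore analysis targets, not only collected data.
- The closing paragraph of that section gives the threshold: "comparative statistics for normally and non-normally distributed data with $p < 0.05$ considered as significant". It then says: "For continuous variables, logistic regression will be used to determine the value of significance to variables with postoperative outcomes".
- Neither the aims nor the analysis section gives a deciding time point, a summary over the three times, a repeated-measures model or a multiplicity rule for spirometry.

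**The concern.** One component of Aim 3 becomes three numbers per patient, and the plan does not say how they produce one answer. There are two gaps.

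First, the named method does not fit. Logistic regression models a binary response. It does not estimate a difference in mean volume between arms, and as written it makes no provision for several readings from one patient. An analyst would probably fall back on the general wording about comparative statistics and run a two-group test at each time.

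Second, if that happens, any of three results can be cited as improvement. A finding such as significance at 48 h only would have no prespecified interpretation, and the error rate for the component would exceed that of one test.

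The three tests could also rest on different patients. The documents expect some patients to be intubated during pain scoring, since they provide a separate scale for them. Participation ends at discharge, and data elements absent from the record do not count as protocol deviations. Some missing readings are therefore foreseeable, although no rate is given.

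**Working it through.** **Plan's own figure.** There is nothing to reproduce beyond the 0.05 threshold. The total of 150 patients has no stated effect size, SD or power, and no error rate is given for a component measured several times.

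**Inputs from the documents.** Three readings (24, 48, 72 h); threshold 0.05; 150 patients randomized 1:1, so 75 per arm if all are randomized.

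**Assumptions.** Two-sided tests (sidedness is not stated); one between-arm test per time with an approximately normal statistic; correlation r between readings of 0.5 to 0.9; equal variance at the three times.

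**Step 1: error bounds.** If the tests were independent, the chance of at least one p<0.05 would be 1 − 0.95³ = 14.3%. The upper bound is 3 × 0.05 = 15%. Counting only results that favour treatment, the independent figure is 1 − 0.975³ = 7.3%, against 2.5% for one contrast.

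**Step 2: correlated readings.** These rates come from simulating three correlated normal test statistics (4 million draws for each setting, critical value 1.96) with no true effect. The first and third rows assume equal correlation between all pairs. The second lets correlation decay with time (AR(1)).

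| Assumed r | 0.5 | 0.7 | 0.8 | 0.9 |
|---|---|---|---|---|
| Any two-sided p<0.05, equal correlation | 12.5% | 10.9% | 9.8% | 8.4% |
| Any two-sided p<0.05, AR(1) | 12.9% | 11.4% | 10.3% | 8.8% |
| Any significant result favouring treatment, equal correlation | 6.3% | 5.5% | 4.9% | 4.2% |

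With equal correlation the inflation is 12.5/5 = 2.5 times at r = 0.5 and 8.4/5 = 1.7 times at r = 0.9. The favourable-direction ratios are the same: 6.3/2.5 = 2.5 and 4.2/2.5 = 1.7.

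**Step 3: one averaged contrast.** The mean of three equally correlated readings has (1 + 2r)/3 times the variance of one reading. Take a difference that one reading detects with 80% power, so its standardized signal is 1.96 + 0.84 = 2.80.

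- Same effect at all three times: power = Φ(2.80/√ratio − 1.96).
- Effect at one time only: the average carries a third of it, so power = Φ(2.80/(3√ratio) − 1.96).
- Detectable difference at 75 per arm and 80% power: 2.80 × √(2/75 × ratio), in SDs of one reading. For one reading alone this is 0.457 SD.

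| Assumed r | 0.5 | 0.7 | 0.8 | 0.9 |
|---|---|---|---|---|
| Variance ratio | 0.667 | 0.800 | 0.867 | 0.933 |
| Power, same effect at all times | 93% | 88% | 85% | 83% |
| Power, effect at one time only | 21% | 18% | 17% | 16% |
| Detectable difference (SD) | 0.374 | 0.409 | 0.426 | 0.442 |

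**Step 4: three tests with Bonferroni, for comparison.** Each test uses 0.05/3 = 0.0167, critical value 2.394. Power at a given reading is Φ(2.80 − 2.394) = 66%, whether or not the other readings carry an effect.

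**The case against.** The strongest reply is that item 8 is one line in a list of variables and nowhere says that three tests will be run. That is correct. A reader might infer that the plan commits to three separate tests at 0.05, but the documents do not support it: they leave the comparison undefined. Nor do they say that p<0.05 applies throughout; that word belongs to the descriptive statistics. What survives is that the list and the threshold together permit a test at each time, and nothing prevents selecting among them.

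A reader might also take 12.5% as the risk of a false claim of improvement. It is not, because it counts results in either direction, including those favouring saline. The figure that matches such a claim is about half as large, 6.3% to 4.2%, although its ratio to the nominal rate is the same.

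The preference for an average can be challenged too. Its power advantage needs a similar effect at all three times, which the documents do not establish. For an effect at one reading only, Bonferroni keeps 66% power where the average has 16% to 21%. Naming one time point for inference would also hold the error at 5%. Both remarks stand, and they make the choice a trade-off to be stated in the plan. They do not justify leaving it open.

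Finally, spirometry is a small part of a wider gap. Aim 3 has several components, CAM is also listed at three times and pain at ten, and no multiplicity rule covers them. That stands as well.

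**Conclusion.** The point holds in a limited form. The plan lists three spirometer readings for analysis, names a method for continuous variables that cannot give the between-arm comparison, and does not define which contrast would show improvement. If each time is tested at 0.05, as the natural reading allows, the two-sided error for this component is about 12.5% to 8.4%, and the chance of a false result favouring treatment is about 6.3% to 4.2% against 2.5%. These figures rest on assumed correlations of 0.5 to 0.9, two-sided tests and approximately normal statistics.

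A reader might infer that the trial's main conclusions are compromised. The documents do not support that: spirometry is a supporting outcome under Aim 3, and the opioid comparison does not depend on it. The change should be made because it is cheap and settles how one named component will be judged.

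**What to change.** In Data Analytic Methods, for item 8, replace logistic regression and any per-time testing with one linear mixed model of the 24, 48 and 72 h volumes. Include arm, time and arm-by-time, and model the within-patient correlation. Take the arm difference averaged over the three times, with its 95% CI, as the single spirometry test at 0.05. Show the time-specific differences with intervals, labelled descriptive.

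The cost is plan wording and one standard model on data already being collected. The plan should state the downsides:

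- The power gain, from 80% to about 83–93%, holds only if the effect is similar at all three times. An effect confined to one reading that alone has 80% power would be detected with only about 16–21% power. If the team expects such an effect, it should name that one time point for inference in advance and make the others descriptive.
- The model uses every available reading but assumes that the rest are missing at random. This may fail for patients still ventilated or already discharged, so the number of readings by arm and time should be reported with reasons for absence.
- The change controls error for spirometry only. Multiplicity across the other Aim 3 components needs its own rule, which in turn requires one defined test per component.

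### Early 0-10 pain comparisons cover only patients already extubated, a group formed after randomisation, and the plan has no rule for this

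*Combined protocol and SAP*

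**What the plan says.** Hypothesis/Aims sets pain beside opioid use in its first aim: "To demonstrate decreased postoperative opioid usage and decreased pain scores in the postoperative setting in the treatment group compared to controls".

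The third aim looks for better results on clinical measures tied to opioid use. The list of measures that follows it starts with "time to extubation, incentive spirometer volume, return of bowel function".

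Data Analytic Methods, Postoperative Variables, item 10, fixes ten scoring times for one of its two pain instruments: "Pain Scores (Scale 0-10) at 1, 2, 4, 8, 12, 24, 36, 48, 60, and 72 hours after ICU arrival for extubated patients". Anyone still on the ventilator at one of those times is scored on CPOT instead, which runs from 0 to 8. The Postoperative Variables text under Data elements makes the same split.

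The statistical methods paragraph at the end of Data Analytic Methods refers to "comparative statistics for normally and non-normally distributed data" without naming tests. A later sentence in that paragraph gives the one method named for continuous data: "For continuous variables, logistic regression will be used to determine the value of significance to variables with postoperative outcomes".

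Neither section says how a patient who is still intubated counts in the pain comparison, whether the two scales are kept apart, or how the ten scores are combined.

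**The concern.** Which instrument a patient gets at a given hour depends on whether the tube is out, and that is decided after randomisation. If the block shortens ventilation, as Aim 3 hopes, then at hours close to the usual extubation time the treated arm contributes a larger and differently selected share of its patients to the 0-10 comparison. If pain is also related to when patients are extubated, the arms differ in mean score even when the block does nothing to pain. An early difference, or its absence, could then reflect who had been extubated by that hour.

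The named method does not help. Logistic regression models a binary outcome and gives no between-arm comparison of a 0-10 score.

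**Working it through.** **The plan's own figures.** The plan gives 150 patients randomised 1:1, so 150/2 = 75 per arm, and a 0.05 significance level (taken as two-sided). It gives no effect size, SD, power, extubation time or score mean, so there is no stated figure on this point to reproduce. Everything below is illustrative.

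**Assumed inputs.** No true pain effect. Extubation time counted from ICU arrival, lognormal with log-SD 0.5. Medians 4 h (block) and 6 h (control). Pain SD 2. Correlation 0.4 between pain and log extubation time, so more pain goes with later extubation.

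**Formula.** For hour t, z = (ln t − ln median)/0.5. The share extubated is Φ(z), and λ = φ(z)/Φ(z). Mean pain among extubated patients is μ − SD × ρ × λ. Block minus control is therefore

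bias = SD × ρ × (λ control − λ block) = 0.8 × (λ control − λ block).

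**Hour 4.** Block: z = 0, share 0.500, λ = 0.399/0.500 = 0.798. Control: z = (ln 4 − ln 6)/0.5 = −0.811, share 0.209, λ = 1.376. Bias = 0.8 × (1.376 − 0.798) = 0.46 points.

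**All hours, 4 v 6 h.** False rejection is from a simulated Welch t-test among extubated patients (10,000 trials; a rerun gave 12.3% and 10.8% at hours 4 and 8).

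| Hour | Extubated, block v control | Bias (points) | False rejection |
|---|---|---|---|
| 4 | 0.500 v 0.209 | 0.46 | 12% |
| 8 | 0.917 v 0.717 | 0.24 | 10-11% |
| 12 | 0.986 v 0.917 | 0.10 | 6% |
| 24 | over 0.99 in both | under 0.01 | 5% |

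**Sensitivity.**
- Medians 5 v 6 h: 0.22 points at hour 4, with 6-7% false rejection.
- Correlation 0.2: the bias halves, and rejection is at most about 7%.
- Correlation 0 or equal medians: the bias is exactly zero. A separate simulation with 50% extubated in both arms gave 4.7-5.8% rejection.
- Medians 8 v 12 h: 0.46, 0.35 and 0.10 points at hours 8, 12 and 24, with 12%, 13-14% and 6% rejection. The ratio of medians is again 1.5, so this is the same scenario on a slower clock. It shows that the affected hours move, not that the size is robust.

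**Direction.** With positive correlation the bias is positive, so the block looks worse than it is. At +0.4, simulated rejections favouring the block were 0.2-1.4%, below the nominal 2.5%. A negative correlation reverses the sign.

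**Check of the remedy.** A random-intercept mixed model was fitted to the 24, 36, 48, 60 and 72 h scores (within-patient correlation 0.5 assumed, 4,000 trials per setting). Its contrast stayed within 0.015 points of zero, with 5-6% rejection, for 4 v 6 h, for 8 v 12 h, and when discharge before 72 h differed by arm (10% v 5% or 25% v 10%).

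**The case against.** **Size.** Clear inflation needs a one-third cut in extubation time together with a correlation near 0.4. The documents support neither figure, and Methods, Procedures encourages early extubation for everyone, which may narrow the gap between arms. This stands: with 5 v 6 h, or at correlation 0.2, the effect on the error rate is slight. The size cannot be known in advance.

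**Direction.** A reader might infer that the gap would manufacture a benefit. The documents do not support that. Aim 3 ties extubation time to narcotic use, which suggests, without proving, that more pain goes with later extubation. The bias would then count against the block and could hide a benefit.

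**Pooling.** A reader might also infer that 0-10 and CPOT scores will be averaged together. The plan does not say so, and labelling each scale separately reads more naturally as two measures. Raw pooling would be harmful: at hour 4 with 4 v 6 h, (0.500 − 0.209) × 1 = 0.29 points for each point by which the scale means differ. It is a risk to exclude, not a stated analysis.

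**Role of pain.** Data Analytic Methods puts narcotic usage first and lists pain among the additional variables. That limits the weight of the point. Pain nevertheless remains a named part of Aim 1.

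**General wording.** The reference to tests for normal and non-normal data could cover an ordinary two-sample test. Applied to extubated patients, that is the comparison simulated above, so it does not remove the problem.

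Using a different instrument for intubated patients is not itself a fault.

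**Conclusion.** The concern holds in a limited form. At hours near the usual extubation time, a between-arm comparison of 0-10 scores is made in subsets selected after randomisation. It is biased only if two things are both true: extubation differs by arm, and pain is related to extubation time. The plan hypothesises the first and says nothing about the second.

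Under the assumed 4 v 6 h medians and correlation 0.4, the error is about half a point at worst and is negligible by 24 h. Under milder assumptions it is small, and under equal extubation it is absent. The affected hours, size and direction cannot be fixed from the documents. Opioid use is untouched. The plan should be changed because the remedy is cheap and the named method does not answer the pain question at all. Confidence is medium, since every numerical input except the number per arm and the significance level is assumed.

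**What to change.** In the Data Analytic Methods text:

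1. State that 0-10 and CPOT scores are analysed separately and never pooled as raw scores.
2. For the Aim 1 pain comparison, replace logistic regression with a repeated-measures mixed model (arm, time, arm-by-time) on 0-10 scores. Average the main contrast over times when nearly all patients are expected to be extubated, for example 24-72 h. If extubation runs later, as in the 8 v 12 h case, the start of the window needs a second look.
3. Fix that window before any comparison by arm, by staff without access to assignments. Methods, Procedures lets patients and the blinded coordinator learn the assignment after each discharge, so there is no single unblinding date to rely on.
4. Treat scores absent because of intubation or discharge as missing in the model.
5. Report by arm and time the numbers extubated, still intubated and already discharged.
6. Report earlier scores by instrument, described as conditional on extubation status.

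The cost is SAP wording only; data collection does not change. The downside is that early pain contrasts carry less inferential weight.
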